Hypothesis 1: Measures of psychological stress and systemic inflammatory markers will decrease in response to preoperative exercise compared to standard care.

Hypothesis 2: Preoperative measures of psychological stress and systemic inflammatory markers will be positively correlated with postoperative hospital length of stay and occurrence of readmission in all participants.

II. Background and Significance:

The Problem: Interventions to improve health status in patients with pancreatic cancer are understudied. Health, as defined by the World Health Organization, is “a complete state of physical, mental, and social well-being, and not merely the absence of disease or infirmity.” Pancreatic cancer is often diagnosed at an advanced stage, which has resulted in a 5-year survival rate of less than 5%¹. As such, most research has focused on the disease and curative components of treatment, and not the overall health status of the individual. Investigations of exercise in cancer survivors, an intervention able to address and improve most aspects of health, have specifically focused on cancer populations with high survival rates². Furthermore, advances in the medical treatment of pancreatic cancer have increased 5-year survival rate to 10-30% in patients who

receive surgery³, making this a growing clinical population in which interventions to improve health status are understudied.

The Population: Patients with pancreatic cancer undergoing neoadjuvant therapy. Pancreatic cancer is the fourth leading cause of cancer-related death in the United States, resulting in an estimated 37,390 deaths in 2012⁴. Neoadjuvant therapy (preoperative chemotherapy and radiation) is often prescribed to a subgroup of patients to improve their response to surgery, the best known treatment for the disease. This therapy, however, can reduce physical fitness and function, decreasing the health status of the patient during and after treatment. Reduced preoperative cardiopulmonary fitness may also lead to increased postoperative complications⁵, resulting in further decreases in health status.

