The potential participant population will be individuals who receive a diagnosis of borderline-resectable pancreatic cancer (adenocarcinoma), being treated at the University Hospital Cancer Center. These inclusion and exclusion criteria will apply to participants in both groups.

Inclusion Criteria: Recent (< 4 week) first diagnosis of a borderline-resectable pancreatic adenocarcinoma, assigned to receive neoadjuvant therapy and surgery at University of Colorado Cancer Center, physician clearance to participate in exercise program, and age 21-80 years.

Exclusion Criteria: Any significant comorbid conditions that would interfere with or preclude participation in an exercise intervention, including orthopedic conditions such as advanced osteoarthritis, mobility-limiting amputations or chronic injuries, or mobility-limiting acute orthopedic injuries; advanced rheumatoid arthritis; widespread chronic pain conditions such as fibromyalgia; pulmonary conditions such as chronic obstructive pulmonary disease, emphysema, interstitial lung disease, use of supplemental oxygen; known cardiovascular disease, uncontrolled hypertension, or new cardiac event within the past 6 months. Participants with a second cancer diagnosis at the time of enrollment will be excluded.

Sample size estimation: No studies have previously investigated the effects of preoperative exercise in patients with pancreatic cancer. In patients with lung cancer, a preoperative exercise program reduced hospital length of stay by 4 days compared to usual care⁴⁰. Based on this difference, with a SD of 3, 12 participants would be required in each the experimental and control groups ($\alpha = 0.05$, $\beta = 0.90$ ⁴¹). To account for overall attrition, groups will be increased by 3 participants each, based on a study of preoperative exercise after neoadjuvant treatment in patients with rectal cancer showing an overall attrition of 28%⁴². A total of **30 participants (15 per group)** will be recruited for this study.

C. Study Design and Research Methods

This is a prospective, non-randomized, parallel group, intervention control trial, patterned on a similar pilot study in patients with rectal cancer⁴².

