Recruitment: Participants will be recruited from the University Hospital Cancer Center. Patients with a recent diagnosis (< 4 weeks) of pancreatic cancer will be given information on the study by their treating physicians and asked if they would be interested in participating. If yes, physicians will have patients complete a HIPAA A form to provide study personnel with their name. Study personnel will access the patients' medical records to evaluate the inclusion/exclusion criteria. If these criteria are met, research personnel will meet with the

potential participant at the University of Colorado Cancer Center to provide information about the study. If patients are still interested in participating, the familiarization and possibly first visit will be scheduled. Participants will have the option of combining the familiarization session and Visit 1. All data collected during screening will be destroyed and recollected after obtaining written consent in patients choosing to participate. If the inclusion/exclusion criteria are not met after review of the health record, the patient will be contacted and the exclusion decision will be explained.

Group Assignment: Volunteers meeting the inclusion and exclusion criteria and willing to participate in the exercise intervention will be assigned to the exercise group. The standard of care, non-exercise control group will comprise volunteers who meet the inclusion and exclusion criteria but are unable to commit to participation in the exercise intervention for practical reasons (e.g. barriers in transportation or home location). The use of a non-randomized study design is to maximize patients participating in the exercise program to determine accrual rate, program adherence, and safety while still allowing a non-exercise control group.

Protocol:

[figure not shown]

Figure 1

Figure 1 shows the event timeline of the study, with time points of visits and intervention in relation to diagnosis and surgery. Written informed consent will be obtained by a study investigator during a familiarization period, where participants will have assessments and the exercise investigation explained in-depth. There will be four time points for data collection: pre-intervention (Visit 1), post-intervention and preoperative (Visit 2), 30-day postoperative (data retrieved from electronic health record), and follow-up (Visit 3).

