The timeline for this protocol is estimated at 2 years. Data collection (participant recruitment and intervention) is estimated at 1 - 1.5, after which data will be analyzed and manuscripts prepared.

Data Analysis and Anticipated Outcomes: Groups will be compared on demographic variables such as age and gender. Variables that differ significantly will be included in planned analyses as covariates. Statistical significance will be defined as $\alpha \leq 0.05$, however, results will be interpreted cautiously as is warranted for pilot studies⁴⁴. As we expect to be underpowered to test for statistical interactions, multiple tests will be used to assess differences in baseline measures, change scores, and postoperative outcomes between groups. Change scores will be calculated as the difference between Visit 2 and Visit 1. Groups will be compared using non-parametric exact k-sample permutation tests, which are well suited for small sample sizes as they do not rely on typical normal-theory methods⁴⁵.

Aim 1: The feasibility of implementing this intervention will be assessed by quantifying the accrual rate of patients willing and able to participate in the preoperative exercise intervention and individual patients' adherence to the prescribed exercise program (percentage of scheduled sessions attended). Safety will be determined by the number of non-serious and serious adverse events and relatedness of the events to exercise, as described by COMIRB.

Aim 2: Hypothesis 1 – Baseline physical fitness and function measures and change scores will be compared between groups using exact k-sample permutation tests. We anticipate a significant difference in the changes from Visit 1 to Visit 2, with the Exercise group demonstrating maintained or improved physical fitness and function compared to the Control group, with no differences in baseline measures. A secondary analysis will be used to describe the trajectory of changes in physical function from visits 1, 2, and 3.

Hypothesis 2 – Postoperative outcomes will be compared with exact k-sample permutation tests (hospital length of stay) or Fisher's exact tests (hospital readmission) between the Exercise and Control groups. We anticipate the Exercise group to have a significantly lower hospital length of stay and occurrence of hospital readmission compared to the Control group.

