Exploratory Aim: Hypothesis 1 – Baseline psychological stress and systemic inflammatory status measures and change scores will be compared between groups using exact k-sample permutation tests. We anticipate a significant difference in change scores, with the Exercise group demonstrating decreased (improved) psychological stress and improved systemic inflammatory status (decreased CRP, IL-6, sTNFR1 and IIS; increased IL-10) compared to the Control group, with no differences in baseline measures.

Hypothesis 2 – Spearman correlations will be performed between preoperative measures of psychological stress and systemic inflammatory status and postoperative variables. We

anticipate a significant negative correlation between psychological stress and systemic inflammatory status and postoperative outcomes, with lower levels of stress and inflammation associated with improved outcomes in all participants.

G. Summarize Knowledge to be Gained:

Aim 1: The feasibility of future, larger scale implementation of the preoperative exercise program will be assessed primarily by patient adherence to the program, demonstrating patients' ability and willingness to complete the program. The future study of the intervention will be assessed through the measurement of patient accrual, which will provide a reference for the necessary time frame of future studies.

Aim 2: The analyses performed in this aim will reveal 1) how a preoperative exercise intervention affects physical fitness and physical function prior to and after surgery, and 2) whether a preoperative exercise program is associated with improved postoperative outcomes in patients with pancreatic cancer undergoing neoadjuvant treatment. These analyses will also illustrate typical changes in measures of physical fitness and physical function through analysis of the Standard Care group.

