Exploratory Aim: The analyses performed in this aim will reveal 1) how a preoperative exercise intervention effects subjective and objective measures of psychological stress, autonomic function, and systemic inflammation prior to and after surgery, and 2) whether these preoperative measures predict postoperative outcomes in patients with pancreatic cancer undergoing neoadjuvant treatment. These analyses will also illustrate typical changes in measures of physical fitness and physical function through analysis of the Standard Care group. Results from this aim may also lead to the development of novel interventions, if measures are predictive of outcomes but not adequately changed by exercise.

Outcomes from this study will add to the growing body of literature on the effectiveness of preoperative exercise programs in cancer survivors, as well as demonstrate the potential effectiveness of an exercise intervention in patients with pancreatic cancer, where there is limited evidence. By examining potential mediators in the effectiveness of exercise on postoperative outcomes, it allows future studies to tailor exercise program components to focus on the mediators most strongly associated with positive outcomes.

H. References:

- 1 Jemal, A. *et al.* Global cancer statistics. *CA Cancer J Clin* **61**, 69-90, doi:10.3322/caac.20107 (2011).
- 2 Schmitz, K. H. *et al.* American College of Sports Medicine roundtable on exercise guidelines for cancer survivors. *Medicine and science in sports and exercise* **42**, 1409-1426, doi:10.1249/MSS.0b013e3181e0c112 (2010).
- 3 Saif, M. W. Controversies in the adjuvant treatment of pancreatic adenocarcinoma. *JOP* **8**, 545-552 (2007).
- 5 Chandrabalan, V. V. *et al.* Pre-operative cardiopulmonary exercise testing predicts adverse post-operative events and non-progression to adjuvant therapy after major pancreatic surgery. *HPB (Oxford)* **15**, 899-907, doi:10.1111/hpb.12060 (2013).

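### The exploratory stress and inflammation correlations pool both groups without accounting for group, so they cannot tell a mediator from a marker that exercise merely also changes

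*Combined protocol and SAP*

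**What the plan says.** Section I, Exploratory Aim, Hypothesis 2 states that preoperative stress and inflammatory measures "will be positively correlated with postoperative hospital length of stay and occurrence of readmission in all participants". Section IV.F gives the method: "Spearman correlations will be performed between preoperative measures of psychological stress and systemic inflammatory status and postoperative variables". It repeats the analysis set in the anticipated result, "with lower levels of stress and inflammation associated with improved outcomes in all participants". Section IV.C labels the relevant time point "post-intervention and preoperative (Visit 2", so the marker is measured after the exercise programme.

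Two other hypotheses predict a group difference on each side of this correlation. For the markers, section IV.F anticipates a difference "with the Exercise group demonstrating decreased (improved) psychological stress and improved systemic inflammatory status". For the outcome, it says "We anticipate the Exercise group to have a significantly lower hospital length of stay". The sample size paragraph in section IV.B takes its effect from a lung cancer study in which "a preoperative exercise program reduced hospital length of stay by 4 days compared to usual care", with an SD of 3.

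Nothing brings group into the correlations. The covariate rule in section IV.F concerns demographic variables that differ between groups. The covariates in section IV.E (duration of exercise and of neoadjuvant therapy) are for the fitness, function and stress outcomes. Section IV.G then says the results will show whether the measures predict postoperative outcomes, and that future programmes can be directed at the mediators most strongly tied to good outcomes.

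**The concern.** When two groups differ in the mean of both variables, pooling them produces a correlation that comes from the groups alone. Here the conditions for that are what the plan itself predicts: lower stress and inflammation, and shorter stay, in the exercise group. Group assignment adds a second route. Controls are patients who could not commit to the programme for practical reasons such as transport or home location, and section IV.E accepts that selection bias and baseline differences are possible. An existing difference on both variables would act in the same way.

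What is at stake is the use made of the coefficient. A marker that exercise changes but that has no bearing on recovery can show the same pooled correlation as a true mediator. The group-driven part is also largest for the markers that exercise changes most, so a ranking of markers by pooled correlation leans towards those whether or not they matter for outcome.

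**Working it through.** **1. The plan's own figure.** Inputs from section IV.B: difference 4 days, SD 3, α = 0.05, and 0.90 read as power (it is printed as β). With the two-sided normal approximation, n per group = 2(1.960 + 1.282)² × (3/4)² = 2 × 10.51 × 0.5625 = 11.8, which rounds up to the stated 12. The standardised effect on stay is d₂ = 4/3 = 1.33. Recruitment is 15 per group.

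**2. Correlation produced by group alone.** Take two equal groups, a marker difference of d₁ SD, a stay difference of d₂ SD, and no association within groups. The pooled Pearson correlation is

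r = (d₁d₂/4) / √[(1 + d₁²/4)(1 + d₂²/4)].

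For d₁ = 0.8 and d₂ = 1.33: r = 0.267 / √(1.16 × 1.444) = 0.267 / 1.294 = 0.206. For d₁ = 0.5, 1.0 and 1.33, r = 0.135, 0.248 and 0.308. The formula does not depend on whether exercise or self-selection caused the difference.

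**3. How often the pooled test is significant.** The documents give no marker effect, so d₁ is an assumption, shown as a range. Simulation used 20,000 replicates per setting, normal data, zero within-group association, and Spearman tests at two-sided 0.05. The entries are the percentage significant.

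| Marker effect (SD) | 0 | 0.25 | 0.5 | 0.8 | 1.0 | 1.33 |
|---|---|---|---|---|---|---|
| 4 days, 12 per group | 4.9 | 6.0 | 9.2 | 17.1 | 23.0 | 34.7 |
| 4 days, 15 per group | 4.9 | 6.7 | 11.8 | 20.2 | 28.5 | 42.1 |
| 2 days, 12 per group | 5.2 | 5.4 | 6.4 | 7.9 | 10.2 | 13.5 |
| 2 days, 15 per group | 4.9 | 5.7 | 6.7 | 9.7 | 12.1 | 15.4 |

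Repeat runs moved entries by up to about one percentage point. I therefore quote the ranges for 0.5 to 1.33 SD as about 10% to 34% (12 per group) and 11% to 42% (15 per group) with a 4-day effect, and about 6% to 15% with a 2-day effect.

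**4. Shape of the data.** With skewed, whole-day stay (gamma; assumed means 12 and 8, SD 3) at 15 per group, the rates for 0.5 to 1.33 SD are 11%, 21%, 29% and 44%. Normality does not drive the result.

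**5. Group-adjusted test.** Rank both variables over all participants, subtract each group's mean rank, correlate the residuals, and refer t = r√[df/(1 − r²)] to df = N − 3 (21 at N = 24, 27 at N = 30). The mean coefficient is about 0.00, and 4.7% to 5.3% of tests are significant in every setting above.

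**6. Price of adjustment.** Suppose the marker carries the whole exercise effect, with within-group r = 0.4 and a marker effect of 1 SD (both assumed). Power falls from about 54% (pooled) to 44% (adjusted) at 12 per group, and from about 66% to 54% at 15.

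**The case against.** The strongest reply is that the plan's hypothesis is about all participants, and that in step 2 the pooled correlation really is non-zero. Rejecting zero is then a correct statement about marginal association, and a marker can predict outcome even when treatment explains the link. This stands. A reader might infer that the rates in step 3 are false-positive rates for the stated hypothesis. They are errors only if the result is read as a within-group association or as mediation.

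A reader might also infer that the correlations would misdirect the new interventions mentioned in section IV.G. The documents do not support this, because that use is confined to the case "if measures are predictive of outcomes but not adequately changed by exercise". The exercise route needs exercise to change the marker, and with no marker effect the pooled test holds at about 5%. Only an existing group difference could distort that case, and its size is unknown. The mediator sentence is what remains.

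A third tempting reading is that the plan predicts a 4-day reduction in this population. Aim 2, Hypothesis 2 gives no number. The 4 days is a lung cancer figure used for sample size, and section IV.E warns that the resulting sample may prove too small. The 2-day rows are there for that reason.

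Finally, the aim is labelled exploratory, the plan promises cautious interpretation, it speaks of potential mediators, and it plans no formal mediation analysis. This lowers the weight of the point. It does not remove it, since caution about p-values does not separate the within-group from the between-group part of a coefficient.

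**Conclusion.** The point holds as a limit on interpretation. The pooled Spearman correlation is a valid marginal description, but it cannot distinguish a mediator from a bystander marker, and section IV.G uses it for that purpose. The problem is material if exercise or selection separates the groups by about 0.5 SD or more on the marker and stay differs by about the sample-size assumption. It is slight at a marker effect of 0.25 SD (about 6% to 7% even with 4 days) and modest with a 2-day effect.

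The sizes rest on assumed marker effects, equal groups and no within-group association. Readmission, the binary outcome in the same hypothesis, was not simulated. No primary or Aim 2 conclusion depends on these correlations. I rate the point minor to moderate.

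**What to change.** In section IV.F, Exploratory Aim, Hypothesis 2, add that each correlation will be reported in two forms: pooled, and adjusted for study group. The adjusted form can be a partial Spearman coefficient, or a permutation test that permutes within group, which suits the permutation approach used elsewhere in the plan. State that the pooled coefficient describes marginal association only, and that any statement about mediators or independent predictors will rest on the adjusted one. Align the mediator sentence in section IV.G with this.

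The change needs a few lines of text and no new data. Its statistical cost is more than one degree of freedom. The adjusted coefficient leaves out the between-group part of the association, and under full mediation it gives up about 10 to 12 percentage points of power (step 6), which is why the pooled value should stay beside it. Adjustment for group also does not remove confounding within groups, so a non-zero adjusted coefficient would still be only suggestive of mediation.

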The Intervention: A preoperative exercise program during neoadjuvant treatment, which can improve patient health status during and after treatment. Preoperative exercise has been shown to be safe and effective at improving physical fitness and function, vital components of overall health, in patients with other cancer diagnoses undergoing neoadjuvant therapy⁶, but has not been investigated in patients with pancreatic cancer. Therefore, a gap in the research exists surrounding interventions to improve health status in the growing clinical population of pancreatic cancer survivors. The preoperative neoadjuvant treatment period allows implementation of an exercise program likely to maintain or improve cardiovascular fitness and muscular strength, improving postoperative outcomes and health status, and improved physical function has also been associated with decreases in hospital length of stay and readmission⁷. Beneficial effects of preoperative exercise may be mediated by changes in psychological stress and systemic inflammatory markers. Both increased psychological stress and systemic inflammatory markers have been associated with accelerated disease progression and worsening health status^{8,9}. Both are beneficially affected by exercise^{9,10}, possibly contributing to the overall effects of the exercise intervention. Regardless of effects on disease progression, the beneficial psychological effects of exercise¹¹ can contribute to improved health status.

Preoperative exercise is a safe intervention in patients with advanced cancer. Exercise programs, both pre and postoperative, have been safely implemented in a wide variety of cancer survivors, with few to no adverse events reported¹². Although no studies of preoperative exercise programs for patients with pancreatic cancer have been published, postoperative exercise programs in this population have reported no adverse events^{10,13}. A survey of colorectal surgeons agreed that suitable preoperative exercise programs pose no risk to elderly colorectal cancer patients¹⁴, and a systematic review of exercise during neoadjuvant treatment stated that preoperative exercise was a safe and feasible intervention⁶.

III. Preliminary Studies/Progress Report:

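### No planned analysis relates change in a stress or inflammatory marker to outcome, so a marker that exercise lowers but that predicts stay only through its starting level can look like a mediator

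*Combined protocol and SAP*

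**What the plan says.** **Premise.** Section II (The Intervention) states: "Beneficial effects of preoperative exercise may be mediated by changes in psychological stress and systemic inflammatory markers". Section I likewise speaks of mediation through favourable effects on these measures. Both statements are about change.

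**Marker and outcome.** In IV.F, Exploratory Aim, Hypothesis 2: "Spearman correlations will be performed between preoperative measures of psychological stress and systemic inflammatory status and postoperative variables". Section I adds that the measures are expected to be "positively correlated with postoperative hospital length of stay and occurrence of readmission in all participants", so the two groups are pooled. IV.C (Protocol) attaches the preoperative label to one time point only: "post-intervention and preoperative (Visit 2". IV.F does not repeat the visit number, but Visit 2 is the natural reading.

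**Marker and group.** In IV.F, Exploratory Aim, Hypothesis 1: "Baseline psychological stress and systemic inflammatory status measures and change scores will be compared between groups using exact k-sample permutation tests". Also in IV.F: "Change scores will be calculated as the difference between Visit 2 and Visit 1".

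**Covariates.** IV.F adjusts for demographic variables that differ between groups, and IV.E adds the durations of training and neoadjuvant therapy for some outcomes. Neither names a marker's own Visit 1 value.

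**Use of the results.** IV.G says that the work "allows future studies to tailor exercise program components to focus on the mediators most strongly associated with positive outcomes". It also provides for novel interventions "if measures are predictive of outcomes but not adequately changed by exercise".

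**The concern.** A Visit 2 level carries the Visit 1 level forward. If patients who start with high inflammation or stress stay longer whatever happens during neoadjuvant therapy, the Visit 2 level will correlate with stay even though the change contributes nothing. This occurs within each group, so allowing for group alone does not remove it.

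Mediation needs two links: exercise changes the marker, and that change matters for outcome. Hypothesis 1 addresses the first. Hypothesis 2 does not address the second, because it uses the level and not the change, and no written rule joins the two results. At stake is the use foreseen in IV.G: a later programme could be built around a marker that exercise does move but whose movement does not affect recovery.

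**Working it through.** **1. The plan's own figure.** The documents give no figure for the correlation analysis. The sample sizes used here come from IV.B: a difference of 4 days, SD 3, alpha 0.05 (taken as two-sided) and power 0.90 (the printed beta of 0.90, read as power).

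n per group = 2 × [SD × (z₀.₉₇₅ + z₀.₉₀) / difference]² = 2 × [3 × (1.960 + 1.282) / 4]² = 11.82, rounded up to 12.

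This matches the plan: 24 evaluable, 30 recruited.

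**2. Model (assumptions).** The documents give no marker correlations, so these are assumed and varied.
- Visit 1 marker M1: standard normal.
- Visit 2 marker M2 = ρ·M1 + √(1 − ρ²)·e − δ·(exercise), with ρ the Visit 1-Visit 2 correlation.
- Outcome Y = b·M1 + √(1 − b²)·u. Only the starting level matters; the change has no effect.
- δ = 0 (exercise does nothing to the marker) or 1 SD.
- Hypothesis 1 is approximated by a t-test on M2 − M1. "Both" in the table means both tests at p ≤ 0.05; this joint reading is mine, since the plan has none.

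**3. Why the raw correlation is not zero.** With δ = 0, corr(M2, Y) = ρ × b = 0.7 × 0.5 = 0.35. Given M1, the numerator of the partial correlation is 0.35 − 0.7 × 0.5 = 0.

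**4. Results at b = 0.5 (8,000 trials per row).** Adjusted means a partial Spearman given Visit 1 and group.

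| n | δ | ρ | Planned | Hyp. 1 | Both | Adjusted | Adjusted and Hyp. 1 |
|---|---|---|---|---|---|---|---|
| 24 | 0 | 0.5 | 19.4% | 4.9% | 1.1% | 5.0% | 0.2% |
| 24 | 0 | 0.7 | 36.2% | 4.8% | 1.7% | 5.0% | 0.3% |
| 24 | 0 | 0.9 | 55.5% | 4.8% | 2.6% | 5.8% | 0.3% |
| 24 | 1 SD | 0.5 | 16.2% | 65.4% | 9.9% | 4.9% | 3.3% |
| 24 | 1 SD | 0.7 | 29.1% | 85.2% | 24.1% | 4.9% | 4.1% |
| 24 | 1 SD | 0.9 | 44.2% | 100% | 44.2% | 5.3% | 5.3% |
| 30 | 1 SD | 0.7 | 36.0% | 92.9% | 33.1% | 5.3% | 4.9% |

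Repeat runs of the two ρ = 0.7, 1 SD settings put the joint figure at about 23% (n = 24) and 32% (n = 30). The differences of about one point are simulation error.

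**5. Range.** Over ρ = 0.5 to 0.9 and b = 0.3 to 0.7, a marker moved 1 SD by exercise passes both planned analyses in 5% to 78% of trials at n = 24 and 7% to 87% at n = 30. The adjusted correlation plus Hypothesis 1 passes it in about 3% to 6%.

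**6. Planned correlation alone.** With 20,000 trials, n = 24, b = 0.5 and no exercise effect, it is significant in 20%, 35% and 45% of trials at ρ = 0.5, 0.7 and 0.8. At ρ = 0.7 the average rho is 0.32, against 0.02 adjusted for Visit 1, with about 5% significant.

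**7. When the marker does matter (n = 24, effect 0.5).**
- If only the change drives outcome (ρ = 0.7): 37% significant as planned, 60% adjusted for Visit 1.
- If the Visit 2 level itself drives outcome: about 66% as planned; 53%, 40% and 31% adjusted for Visit 1 at ρ = 0.5, 0.7 and 0.8.

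**8. Raw change score.** Correlating M2 − M1 with outcome is not a clean substitute. It is significant in 6% to 44% of trials across these settings although change has no effect, because change is itself correlated with the starting level.

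**The case against.** The strongest reply is that the plan never claims to select mediators this way. IV.F contains no ranking, threshold or selection step. The sentence in IV.G is a closing remark about future studies, and the same section frames the analysis question as prediction, which a Visit 2 correlation answers properly. This stands: a reader might infer a rule that picks mediators by size of correlation, but the documents contain none.

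A reader might also infer that a marker merely high from the start, and untouched by exercise, would pass as a mediator. Read together, the documents do not support that. Hypothesis 1 tests change scores for the same measures, and IV.G sets apart markers that are "if measures are predictive of outcomes but not adequately changed by exercise". In the simulation such a marker passes both analyses in only about 0.6% to 5% of trials.

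Nor can it be said that the plan systematically favours stable prognostic markers. With one baseline-only and one change-only marker at n = 24, the raw correlation ranks the wrong one first in 27% of trials when both Visit 1-Visit 2 correlations are 0.5, 49% at 0.7, and 63% at 0.8 (56% with 0.8 for the baseline-only and 0.7 for the change marker). The direction depends on a value that the documents do not give.

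Finally, this is an exploratory aim in a 30-person pilot that promises cautious interpretation. That lowers the priority. It does not supply the missing link between change and outcome.

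**Conclusion.** The point holds in a limited form. Hypothesis 1 and the separate category in IV.G deal with most markers that exercise does not change. What remains is a marker that exercise lowers but that predicts stay only through its starting level: it can satisfy both hypotheses, in about 23% of trials at n = 24 and 32% at n = 30 under the central assumptions. The size depends heavily on those assumptions, which include normal data and a correct linear model. The structural gap does not: no planned analysis bears on whether change in a marker matters for outcome, so the mediator wording in IV.G goes further than the analyses can support. No primary result, sample size or safety decision is affected. Low priority.

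**What to change.** 1. In IV.F, Exploratory Hypothesis 2, state that the preoperative value is the Visit 2 value, keep the raw correlation, and label it as answering prediction only.
2. Add, as exploratory, a partial Spearman correlation of each Visit 2 value with length of stay given its own Visit 1 value and group, with a 95% interval. Do not substitute the raw change score.
3. In IV.G, call a marker a candidate mediator only when this adjusted association and the Hypothesis 1 change comparison both point that way. Say that neither removes confounding from the non-randomized assignment. The adjusted figure alone is not enough, since it says nothing about whether exercise moves the marker.
4. The added analysis covers length of stay only. For readmission, either specify a counterpart or make no mediator statement.

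**Cost.** No new data, since IV.C schedules these measures at Visits 1 and 2. One extra analysis per measure and one or two degrees of freedom. Correlations driven by starting level will shrink. Power falls when the preoperative level itself drives outcome (66% raw against 53% to 31% adjusted for Visit 1, and slightly less with group added), so a non-significant adjusted result should not be read as ruling out mediation.
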